### **3.6.3 AD LIBITUM MEAL TEST**

Study participants will be presented with a standardized lunch after their PET-scan days are completed in order to provide objective measure of ad libitum food intake under fasting conditions to correlate with neural, endocrine, and metabolic factors. Subjects will be provided with a standard meal representing an excess of their calculated daily energy requirements from which to select their lunch and told to "Eat as much or as little as you want". Subjects will be limited to no longer than 30 minutes to eat their meal and the amount of time to consume the meal will be recorded. Meal items will be weighed prior to and following consumption in order to obtain an accurate measure of the amount of food, energy and nutrients consumed. Any subsequent meals (not on the final day of admission) will be adjusted to compensate for the amount eaten at lunch to maintain a constant overall daily calorie intake.

### **3.7 Genetic Testing**

Research has identified several candidate genes and single nucleotide polymorphisms (SNPs) that are related to body mass and obesity [59]. Specifically, genome-wide association (GWA) studies of the molecular underpinnings of obesity indicate that body weight is largely influenced by genes expressed within central nervous system tissue [60]. As such, we aim to build upon these findings by collecting DNA samples to search for obesity-associated genes and variations.

DNA samples will be analyzed using blood samples collected (additional 5 mL sample). A portion of the blood samples collected from each subject will be sent to a commercial laboratory for genetic analysis of genes that are related to obesity and dopamine. All other DNA samples will be stored indefinitely at the NIH for future analyses. We plan to perform whole genome or exome sequencing with the stored DNA samples. These analyses may take place years after the samples are obtained.

### **Secondary Genomics Finding Service:**

Secondary (incidental) findings analysis will be performed by the NHGRI-NIHCC-SGFS team under its CLIA license. The exomes or genomes will be analyzed for a particular set of variants or genes that will be determined by the SGFS team. It is critical to recognize that this evaluation is deliberately designed to have a high positive predictive analytic validity (high likelihood that the variant is truly present in the participant and is pathogenic) and very high thresholds for pathogenicity (clinical validity).

If there is a secondary variant identified (current, 2014 estimated yield is that 2-3% of participants will have such a finding), the research participant will then be contacted by the SGFS team to inform them that a genetic finding that requires confirmation with a second sample. If the second sample is positive, the NHGRI consult attending and genetic counselor will review the variant, disclose the finding to the participant, provide medical and genetic counseling for that variant, and provide referrals for further evaluation and follow-up for the proband and recommendations for testing for his/her family members.

DNA samples stored at the NIH will be kept in locked freezers in a secure location. The samples will be coded to protect personally identifiable information and the code key will be retained by the research team. Data from these samples will be deposited into a government health research database after the data have undergone QC, as indicated in this protocol's Genomic Data Sharing Plan. The information in this database will be available only to qualified researchers who have received approval from the NIH Data Access committee. No personal identifiers will be entered into the public database. We will inform subjects of the many safety measures we will use to protect their privacy.

This sample size will also provide  $>80\%$  power to detect a correlation of  $r > 0.4$  between the binding potential of two DA D2 receptor antagonists [ $^{11}\text{C}$ ]raclopride and [ $^{18}\text{F}$ ]fallypride. Our unpublished observations found within subject correlations of  $r \geq 0.6$  for repeated striatal D2BP using [ $^{18}\text{F}$ ]fallypride under different diet conditions. Computational modeling of the PET studies using the known kinetic properties of [ $^{11}\text{C}$ ]raclopride and [ $^{18}\text{F}$ ]fallypride along with various assumptions about within-subject variability in endogenous DA tone suggests that D2BP measured using these antagonists should be significantly correlated with  $r = 0.66 \pm 0.0006$ .

Preliminary analysis indicates that to replicate our preliminary ( $n=13$ ) finding in this cohort of BMI-dependent dopamine release in the ventral pallidum ( $r=0.586$ ;  $p=0.045$ ), a sample size of 21 subjects distributed evenly across 3 BMI strata (to detect  $r>0.6$  at  $p<0.05$  and  $> 80\%$  power). As this pilot data was not available prior to study onset and the intention is to replicate this finding in an independent sample, we require an additional 7 participants in each of 3 BMI strata to achieve this aim (total of 20 participants per strata, inclusive of original 13).

## **5. Safety Considerations**

### **5.1 POSSIBLE RISKS AND HAZARDS**

Research-related risks in this study include those associated with study procedures, namely blood drawing, indirect calorimetry, measurement of body composition by dual energy x-ray absorptiometry (DEXA), air-displacement plethysmography (BodPod), bioelectrical impedance (BIS), administration of doubly labeled water (DLW) for measurement of average total energy expenditure, Beck Depression Inventory-II questionnaire, and positron emission tomography (PET) imaging as well as magnetic resonance imaging (MRI) scanning sessions. There are no study medications.

*Blood drawing.* The placement of intravenous needles may cause transient pain, and may also result in bruising, bleeding, and/or clotting at the site of needle insertion. A medical provider will be available should any of these problems occur. There is a possibility that a catheter placement would be unsuccessful or need to be removed. If this should occur, another catheter would be placed. It is possible that this may occur more than once during the subject's participation in the protocol. We will draw approximately 165mL during the inpatient phase of the study, totaling to roughly 195 mL over 12 months (including maximums of 10 mL non-research blood sampling during screening visit, 10 mL fasting research blood collected during 5-day outpatient dietary stabilization phase, 165 mL during subsequent inpatient stay, and 10 mL at 12 month follow up visit). This estimate falls in the lower end of range of approved research blood draws, which is capped at 550 mL over an 8-week period.

*Continuous glucose monitoring.* According to the device manufacturer, there is minimal risk associated with the device. Possible side effects include but are not limited to local infection, inflammation, pain or discomfort, bleeding at the insertion site, bruising, itching. During clinical studies submitted to the FDA upon approval of this device, there were no infections at the sensor insertion site or adhesive areas and no serious adverse events or unanticipated adverse device effects. Device related adverse events were related to sensor insertion and adhesive area irritations and to pain/discomfort during the wear period. A medical provider will be available should any of these problems occur.

*Indirect calorimetry.* The use of the ventilation hood may cause some minimal discomfort in claustrophobic subjects.

*DEXA.* The amount of radiation during the DEXA scan is less than 1 mrem to the whole body. This amount is less than the radiation exposure received by anyone living in the United States in one day. The use of the DEXA scan apparatus may cause some minimal discomfort in claustrophobic subjects and may cause some minimal back pain in a small minority of the individuals.

*Air-displacement plethysmography (BodPod).* This procedure may cause discomfort in claustrophobic subjects.

*Bioelectrical impedance spectroscopy.* There are no risks involved with this measurement and subjects will not feel the electric current.

*Body weight monitoring.* There are no known risks with intermittent monitoring of body weight.

*Doubly labeled water.* The doubly labeled water procedure has no known risks.

*Eating Disorders Examination Questionnaire (EDE-Q).* There is no known risk associated with this questionnaire; however, there is the potential of discovering clinically relevant information requiring further follow-up. If this is the case, subjects will be referred to their primary care for follow up with an eating disorder specialist as desired.

*National Adult Reading Test (NART-R).* There is no known risk associated with the NART.

*Positive and Negative Affect Scale-X (PANAS).* There is no known risk associated with the PANAS-X.

*UPPS-P Impulsive Behavior Scale (UPPS-P).* There is no known risk associated with the UPPS-P.

*Pittsburg Sleep Quality Index (PSQI).* There is no known risk associated with the PSQI.

*Edinburgh Handedness Inventory.* There is no known risk associated with the Handedness Inventory.

*Ad Libitum Meal Test.* There is no known risk associated with the ad libitum meal test.

*Food frequency questionnaire (FFQ).* There is no known risk associated with the FFQ.

*Three-factor eating questionnaire (TFEQ).* There is no known risk associated with the TFEQ.

*Monetary Choice Questionnaire (MCQ).* There is no known risk associated with the MCQ.

*Barrett Impulsiveness Scale (BIS)*. There is no known risk associated with the BIS.

*Binge Eating Scale (BES)*. There is no known risk associated with the BES.

*Yale Food Addiction Scale 2.0 (YFAS 2.0)*. There is no known risk associated with the YFAS 2.0.

*Beck Depression Inventory (BDI-II)*. There are no known risks associated with the BDI; however, one item on this measure enquires about suicidal thoughts or actions and high-ranging total score can be indicative of severe depression. This questionnaire will be administered in REDCap to facilitate “real-time” score monitoring. If a participant’s score exceeds predefined thresholds, or endorses current suicidal thoughts on this measure during the study (e.g., provides a response of 1 - 3 on question 9), REDCap will be programmed to send an email alert to the study team in real-time, indicating a follow-up response is required. For patients with moderate/mild findings, the clinician may follow up with the appropriate floor’s social work staff:

Social Work Department: [name]

For patients in crisis or who have signs of suicidal ideation, the staff clinician may contact the Clinical Center’s Psychiatric Consultation Liaison Service (PCLS). The social work staff may also contact PCLS if further attention is needed.

*Depression, Anxiety, Stress Scales (DASS-21)*. There is no known risk associated with the DASS-21. This questionnaire will be administered in REDCap to facilitate “real-time” score monitoring. If a participant’s score exceeds predefined thresholds, the research team will be alerted that a follow-up response is required, as described above.

*DSM-5 Self-Rated Level 1 Cross-Cutting Symptom Measure*. There is no known risk associated with this self-report measure. However, there is the potential of discovering clinically relevant information requiring further follow-up. If this is the case, a member of the research team will contact the subject, and appropriate follow up will be planned (e.g., Outpatient Social Work consult, see above).

*State Trait Anxiety Inventory (STAI)*. There is no known risk associated with the STAI.

*Cohen Perceived Stress Scale (PSS)*. There is no known risk associated with the PSS.

*Fagerström Test for Nicotine Dependence (FTND)*. There is no known risk associated with the FTND.

*Satisfaction with Life Scale (SWLS)*. There is no known risk associated with the SWLS.

*MacArthur Socioeconomic Status (SES) Questionnaire*. There are no known risks associated with the MacArthur SES questionnaire although some subjects may find completing the task tedious or some may find the questions probing and too personal in nature to comfortably answer. Subjects will be informed that they do not have to respond to all the questions if they have reservations about sharing such personal information.

*Internal state visual analog scales.* There are no known risks associated with the visual analog scale assessment of hunger, satiety/fullness, or intensity ratings of hunger, fullness, nausea, or pain.

*Delay discounting computer procedure.* There is no known risk associated with the assessment of delay discounting by computer.

*Assessment of liking and wanting of food.* There is no known risk associated with assessment of liking and wanting of food.

*Apathy Motivation Index.* There is no known risk associated with this assessment of motivation.

*Big 5 Personality Test.* There is no known risk associated with this assessment of personality traits.

*Self reported Habit Index.* There is no known risk associated with this assessment of habit.

*Creature of Habit Scale.* There is no known risk associated with this assessment of habit.

*Reward based Eating Drive Scale.* There is no known risk associated with this assessment of eating behavior.

*Food Go/No-go computer task.* There is no known risk associated with the go/no-go computer task.

*Slips of Action Paradigm/Fabulous Fruit Task.* There is no known risk associated with the slips-of-action paradigm, assessed by the FFT computer task.

*Liking Survey.* There is no known risk associated with the liking survey.

*Eye tracker.* There is no known risk associated with the eye tracker device.

*Reward Prediction Error Task.* There is no known risk associated with the RPE computer task, though participants may find the task to be tedious.

*Physical activity monitors.* There are no risks associated with the monitors, but subjects may find them to occasionally be inconvenient.

*Positron emission tomography.* This research study involves exposure to radiation from the radioactive tracers [F]fallypride and [C]raclopride, as well as the transmission scans. The total amount of radiation subjects will receive in this study is from one injection of approximately 5 mCi of [F]fallypride and two injections of approximately 20 mCi of [C]raclopride. The NIH Radiation Safety Committee has reviewed the use of radiation in this research study.

Using the standard way of describing radiation dose, from participating in this study, subjects will receive a total of 6.88 rem to their gallbladder wall, 3.65 rem to their urinary bladder wall, and 3.92 rem to their liver. All other organs will receive smaller amounts of radiation. Although each

organ will receive a different dose, the amount of radiation exposure study subjects will receive from these procedures is equal to a uniform whole-body exposure of 1.22 rem. The amount of radiation received in this study is within the dose guideline established by the NIH Radiation Safety Committee for research subjects. The guideline is an effective dose of 5 rem (or 5,000 mrem) received per year. The average person in the United States receives a radiation exposure of 0.3 rem per year from natural sources, such as the sun, outer space, and the earth's air and soil. While there is no direct evidence that the amount of exposure received from participating in this study is harmful, there is indirect evidence it may not be completely safe. There may be a very slight increase in the risk of cancer.

A pregnancy test will be performed on the first day of admission for all female participants. If subjects are pregnant or breast feeding, they may not participate in this research study. It is best to avoid radiation exposure to unborn or nursing children, since they are more sensitive to radiation than adults.

*Magnetic resonance imaging.* People are at risk for injury from the MRI magnet if they have pacemakers or other implanted electrical devices, brain stimulators, some types of dental implants, aneurysm clips (metal clips on the wall of a large artery), metallic prostheses (including metal pins and rods, heart valves, and cochlear implants), permanent eyeliner, implanted delivery pump, or shrapnel fragments. Welders and metal workers are also at risk for injury because of possible small metal fragments in the eye of which they may be unaware. Subjects will be screened for these conditions at their outpatient screening visit and will be excluded if there is any indication of ferrous metal implants. They will also be screened again before having the scan per standard procedure and if they indicate any ferrous metal implants, they will not receive an MRI scan. In addition, all magnetic objects (for example, watches, coins, jewelry, and credit cards) will be removed before entering the MRI suite.

It is not known if MRI is completely safe for a developing fetus. Therefore, all women of childbearing potential will have a pregnancy test performed within 24 hours of scanning. The scan will not be done if the pregnancy test is positive. People with fear of confined spaces may become anxious during an MRI. Those with back problems may have back pain or discomfort from lying in the scanner. The noise from the scanner is loud enough to damage hearing. Subjects should not have a research MRI scan if they know that they have hearing loss. Everyone having a research MRI scan will be fitted with hearing protection. If it is difficult for subjects to tolerate the confinement or the noise within the scanner they will be taken out immediately if they so request. There are no known long-term risks of MRI scans.

*Genetic testing.* The results of genetic testing may identify a genetic mechanism relevant to obesity or other metabolic disorders. This testing may also result in the incidental finding of a genetic condition that is unrelated to obesity or metabolism. Disclosure of this information may be upsetting to some participants. The participant may seek additional testing, genetic counseling, and relevant treatment with her/his health care providers. In addition, there is the potential for other individuals outside of the study to gain access to personal information about the participants from their genetic data. This study and the NIH have extensive safeguards in place to prevent individuals from accessing this type of information. Sequencing information and basic phenotypic information (e.g., age, sex, race) will be stored on a secure database at the NIH, where access is restricted to

pre-approved researchers. Participants will be notified if there is evidence that personal information has been compromised.

Finally, information gained from genetic testing, if used outside of the study, could negatively impact an individual's ability to obtain health insurance, life insurance, or a job. Should genetic testing lead to the diagnosis of a genetic condition unrelated to obesity or metabolism, the participant may be required to disclose this information to potential insurance providers. The Genetic Information Nondiscrimination Act (GINA) is a federal law that generally criminalizes discrimination of individuals based on genetic information by companies, group health plans, and most employers. According to this law, health insurance companies or group health plans (as of May 21, 2010) cannot request an individual's genetic information or use it to make decisions about eligibility or premiums; employers cannot use genetic information in hiring, promotion, or firing decisions, or in setting terms of employment (as of Nov 21, 2009).

The study team will discuss these circumstances with the participant, should s/he inquire about them.

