## **2. Study Design and Methods**

[figure not shown]
This study will investigate adult volunteers, stratified by BMI who will be invited to participate in 2 PET scan sessions. Thirty-nine volunteers will be examined while admitted as inpatients to the Metabolic and Clinical Research Unit (MCRU) at the NIH Clinical Center. In advance of the first PET session, interested volunteers will be pre-screened via telephone, and those deemed potentially eligible for the study will be invited to the Clinical Center to provide informed consent, complete a medical evaluation, and complete cognitive testing. Subjects will be required to consume a standard diet provided by the NIH Clinical Center for up 5 days prior to the inpatient visit.

Upon completion of the inpatient portion of the study, participants will be asked to complete 13 days of outpatient monitoring of weight, activity and energy balance (via doubly labeled water). Finally, participants will be invited to complete a 1-year follow-up assessment approximately 12 months after the final scanning session. Subjects will be asked to complete physical activity and body weight monitoring during the 12 months between their inpatient visit and 1-year follow up outpatient visit. The NIH will provide commercial accelerometers and scales to the subjects to enable remote monitoring. Additionally, during this 12-month period, participants will be provided with research grade accelerometers for periodic 7-day actigraph assessments. Subjects will be invited back to the NIH for MRI data acquisition and body weight measurements at the one-year follow up mark.

**Table 1** and **Figure 2** indicate the timeline for eligible volunteers who have consented to participating in PET scanning. Scan conditions (e.g., [F]fallypride, and [C]raclopride/‘milkshake challenge’) will be counterbalanced across subjects.

**Table 1.** Example PET study timeline, including outpatient screening, inpatient procedures, outpatient monitoring, and 1-year follow-up assessments. The order of [ $F^{18}$ ]fallypride or [ $C^{11}$ ]raclopride/ milkshake challenge scan for the 2 inpatient scan days will be randomized to the extent possible given PET department scheduling constraints. Phase B of the study will occur as up to 11 contiguous inpatient days although to minimize volunteer burden, volunteers may opt to schedule Phase B as two or three separate two-day inpatient visits.

	Phase A	Phase B		Phase C	Phase D

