### **2.3.3 INPATIENT NEUROIMAGING SCHEDULE (PHASE B)**

Based on the screening visit (Phase A), consenting volunteers will be scheduled for study Phase B (inpatient visit to the MCRU at the NIH Clinical Center), preceded by up to 5 days of dietary stabilization as described above. This phase (B) of the study will occur as up to 6 contiguous inpatient days (depending on facility availability). To control for the impact of gonadal hormones on food intake, every effort will be made so that female subjects of reproductive potential will be admitted during the follicular phase of their menstrual cycle.

Following admission for Phase B, volunteers will undergo metabolic measurements consisting of: body weight and height; measurement of body composition (e.g., dual energy x-ray absorptiometry (DEXA), air-displacement plethysmography (BodPod)) and they will complete a battery of self-report questionnaires and computer tasks related to mood, stress, thoughts about food and eating, and self-control. Female subjects of reproductive potential will also complete a urine pregnancy test on Day 1 of the inpatient visit and interviewed about the possibility of pregnancy. Positive test results will preclude subjects from further participation. The purpose of these measurements is to facilitate examination of exploratory aims by providing a comprehensive assessment of whole-body composition in the subjects, as well as measures of cognitive processes that subserve typical food intake and feeding behaviors. The baseline measurements will then be compared with similar measurements during the 1-year follow-up. Except where noted, subjects will be provided a standard breakfast, lunch and dinner (approximately 50% calories from carbohydrate, 35% from fat and 15% of calories from protein) along with coffee/tea or diet soda in accordance with their usual intake.

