While at the MCRU, after an overnight fast, the participant may undergo indirect calorimetry to assess resting energy expenditure. The participant may be dosed with doubly labeled water and initial urinary samples may be collected. A member of the research team will instruct the participant on procedures for urinary collection, activity and weight monitoring during the outpatient phase (Phase C). The participant may be provided with accelerometers and a scale to track body weight at home. A member of the research team will discuss with the subject to schedule any remaining neuroimaging sessions, if applicable. Female participants will be scheduled to complete scanning, ideally within the follicular phase of their menstrual cycle to control for the effects of gonadal hormones on feeding behavior. Because inter-individual variability in menstrual cycle length has been reported, follicular phase will be adjusted by the average length of each woman's menstrual cycle. On average, the follicular phase in adult women is 15 days in length, so every effort will be made to admit women for their inpatient stay within 10 days of the first day of menstruation.

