### **Neuroimaging of Dopamine Transmission in Obesity**

EVENT	AMOUNT	OCCURANCE	TOTAL
Outpatient per diem (1 screening visit + Up to 5 days stabilization diet)	\$20	Up to 6	Up to \$120
Outpatient per diem (after 1 st hour)	\$10	5-7	\$ 50-70
Inpatient per diem (up to 5 days diet stabilization + up to 6 days testing)	\$40	Up to 11	Up to \$ 440
Body composition (e.g.,DEXA, Bod-Pod, BIS)	\$50	1	\$50
Indirect calorimetry	\$25	1	\$25

Blood draws (1 screening; 7 inpatient)	\$20	8	\$160
Continuous glucose monitoring	\$20	5	\$100
PET	\$100	3	\$300
MRI Session(s)	\$100	Up to 2	Up to \$200
Psychophysical Taste Test	\$20	1	\$20
Computer tasks	\$10	5	\$50
Eye movement	\$10	2	\$20
Psychological/cognitive testing and questionnaires	\$10	19	\$190
Doubly labeled water administration	\$25	1	\$25
Outpatient urine sampling	\$10	13	\$130
Physical activity/weight monitoring (outpatient)	\$250	1	\$250
	Total		\$1530-2150
		Compensation:	

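### PET is tied only to an admission-day pregnancy test while MRI requires one within 24 hours, so a PET session can follow the test by up to 5 days in a 6-day stay

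*Combined protocol and SAP*

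**What the plan says.** The test linked to PET appears in two places. The PET paragraph of Section 5.1 states: "A pregnancy test will be performed on the first day of admission for all female participants". Section 2.3.3 has female subjects of reproductive potential "complete a urine pregnancy test on Day 1 of the inpatient visit", together with an interview about possible pregnancy; a positive result ends participation. Neither place limits the time from test to injection. The screening list in Section 2.3.1 and Table 1 contain no pregnancy test.

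The MRI paragraph of Section 5.1 has a different rule: "all women of childbearing potential will have a pregnancy test performed within 24 hours of scanning". The scan is cancelled if the test is positive.

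The length of stay is given in more than one way. Section 2.3.3 says: "This phase (B) of the study will occur as up to 6 contiguous inpatient days". The Table 1 caption in Section 2 says: "Phase B of the study will occur as up to 11 contiguous inpatient days". The remuneration table in Section 12 is consistent with the longer figure, counting up to 5 inpatient diet days plus up to 6 testing days. The caption also says that "volunteers may opt to schedule Phase B as two or three separate two-day inpatient visits", and Section 2.3.3 lets staff "schedule any remaining neuroimaging sessions, if applicable".

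Each participant has two PET sessions. Their order and dates depend on the PET department and on radiopharmacy production (Section 2.3.3).

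**The concern.** Section 5.1 bars pregnant women from the study because unborn children are more sensitive to radiation than adults. PET here means three tracer injections (one fallypride, two raclopride) and a stated whole-body equivalent of 1.22 rem. For MRI, the protocol says only that complete safety for a fetus is not known. Yet MRI has a test tied to the scan, while PET has one tied to admission. The protocol gives no reason for the difference.

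What is at stake is participant safety: a woman could receive the tracers several days after her only required PET-related test, with every written rule followed. The statistical analysis is not affected.

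**Working it through.** The plan states no figure for this interval, so there is none to reproduce. The check is a day count from the rules as written.

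**Inputs**
- Test day: Day 1 of the inpatient visit (Section 2.3.3), or first day of admission (Section 5.1, PET).
- Stay: up to 6 days (Section 2.3.3); up to 11 days if the diet is taken as an inpatient (Table 1 caption; Section 12); or two or three separate two-day visits (Table 1 caption).
- PET: two sessions on two inpatient scan days that are not fixed in the text. Preparation starts at about 9:00 AM (Section 3.1.2).
- MRI comparison: 24 hours (Section 5.1).

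**Formula:** longest compliant gap = last possible inpatient day − test day.

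| Schedule | Calculation | Longest gap |
|---|---|---|
| 6-day stay, test on Day 1 | 6 − 1 | 5 days |
| 11-day stay, test on first diet day | 11 − 1 | 10 days |
| 11-day stay, test after 5 diet days | 11 − 6 | 5 days |
| Two-day visit, every admission tested | 2 − 1 | 1 day |
| Split visits, only first admission tested | no limit in the text | not bounded |

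**How easily 24 hours is exceeded.** In one contiguous stay, a session on Day 3 starts preparation at about 9:00 AM. Even a test at the very end of Day 1 precedes that by 24 + 9 = 33 hours. A single Day 1 test can therefore fall within 24 hours of both sessions only if PET occupies Days 1 and 2.

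**After the change.** With the MRI rule applied to each PET session, the longest gap is 24 hours under every permitted schedule.

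**Number of added tests.** There would be at most 2 per woman, one for each PET session. With up to 60 participants (Section 2.1) and about half women (the protocol's expectation in Section 7.1), this is 2 × (60 × 0.5) = 60. At the accrual ceiling of 100 it is 2 × (100 × 0.5) = 100. The half is an expectation and not a cap; if every participant were a woman, the figures would be 2 × 60 = 120 and 2 × 100 = 200.

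**The case against.** The contrast with MRI may have an ordinary explanation. MRI is repeated at the 12-month outpatient visit, where there is no admission, so its rule has to be tied to the scan. PET happens only after an admission. The PET paragraph also covers all female participants, whereas the MRI rule covers women of childbearing potential, and a positive Day 1 test ends participation instead of only cancelling a scan. This explanation is plausible, but the protocol does not give it, and it does not shorten the gap.

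Five days is a worst case, with PET on the last day of a maximum-length stay. Figure 2, the example schedule, is not shown, so the usual gap is unknown. That is right, and 5 days should be read as an upper bound. The 10-day case is weaker still: Table 1 puts the diet and the inpatient visit in separate columns, which suggests that Day 1 follows the diet. It stands only as a conditional reading. Likewise, the first day of admission can naturally be read as the first day of each admission, which would hold split visits to a 1-day gap. The text does not say so.

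Other safeguards exist: exclusion and withdrawal for pregnancy, the interview, every effort to admit women within 10 days of the start of menstruation, and tests linked to up to two MRI sessions. They make the absolute risk probably low. None is a condition for a PET session, and an MRI test falls near a PET day only by chance. The Radiation Safety Committee reviewed the radiation use, and PET department procedures not seen here may add a scan-day check. The protocol itself requires none.

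**Conclusion.** The concern holds. As written, a PET session can follow the only PET-linked pregnancy test by up to 5 days in a 6-day stay, against 24 hours for MRI. The 10-day figure applies only if Day 1 is the first inpatient diet day. In split visits the gap is at most 1 day if every admission is tested, and is not bounded by the text if only the first is.

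These limits assume that PET may fall on any inpatient day, since the text does not fix it. The documents give no fetal dose and no basis for estimating how often a pregnancy would be missed, so the size of any harm cannot be stated. The change should be made because it tightens protection for the procedure the protocol says to avoid in pregnancy, at very small cost.

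**What to change.** In Section 2.3.3 and in the PET paragraph of Section 5.1, apply the existing MRI rule: a negative urine pregnancy test within 24 hours before each PET session, at every admission, and no PET session if the test is positive. Adding a pregnancy-test row to Table 1 would keep the schedule consistent with the text.

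The cost is two wording changes (plus the optional table row) and the small number of urine tests worked out above. Fewer are needed wherever the Day 1 or MRI test already falls within 24 hours before PET. The design, sample size and analysis do not change.
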